areas as the solution can cause irritation and sensitization. A review of chlorhexidine hypersensitivity stated possible reactions include contact dermatitis, contact urticaria, and anaphylaxis.⁶ There has also been a case report of desquamating vaginal epithelium with chlorhexidine that resulted in the planned surgery being cancelled. The patient was treated with steroids, antihistamines, and topical estrogen and the vaginal mucosa was well healed within two weeks.⁷ One study conducted in South Africa looked at the tolerance and safety of different concentrations of chlorhexidine for peripartum vaginal washes. The study concluded that those receiving 4% chlorhexidine gluconate washes had more vaginal irritation than those receiving 1% or 0.25%.⁸ Nevertheless, another study showed that non-pregnant women were able to tolerate 4% chlorhexidine gluconate solution.⁹ In fact, the American Congress of Obstetricians & Gynecologists issued a committee opinion in 2013, advocating that chlorhexidine gluconate with low concentrations of alcohol are both safe and effective for off-label use as surgical preparations of the vagina.¹⁰

Currently, surgical site infections at Northwestern's Prentice Women's Hospital are higher than the national average. One way to combat this would be to use more effective preoperative antiseptic agents. Chlorhexidine gluconate is used for surgical preparation of the vagina in patients allergic to iodine, but its application can be far-reaching. The significance of the data from this proposed study will allow us to determine the tolerance of 4% chlorhexidine gluconate compared to povidone iodine, and whether chlorhexidine gluconate is not only superior in its antiseptic properties, but also similarly or possibly more tolerable than povidone iodine.

INCLUSION & EXCLUSION CRITERIA:

Inclusion criteria: Women over age 18 who have the ability to understand and willingness to sign a written informed consent and are undergoing:

1. undergoing hysteroscopy
2. gynecologic dilation & curettage
3. endometrial ablation
4. Essure without concomitant laparoscopy

Exclusion criteria: Women who are:

1. pregnant
2. have a history of atopic dermatitis, vaginal irritation, allergic reactions, or anaphylaxis to chlorhexidine gluconate or povidone iodine.

STUDY ANALYSIS PLAN:

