The study will take place at a single site, Northwestern Prentice Women's Hospital. Using a 2-sided test to detect a difference between proportions with 80% power and a 5% significance level, and assuming the prevalence of irritation in the control group (povidone iodine) is 10% and prevalence of irritation in the exposed group (chlorhexidine gluconate) is 31%, and factoring in patients lost to follow up given that the data collection is through a survey, the study will need 68 participants in each group. There are an estimated 800 hysteroscopies at Prentice Women's Hospital each year and given incomplete follow-up, we estimate it will take 6 to 8 months of patient enrollment to achieve this desired sample size.

STUDY-WIDE RECRUITMENT METHODS:

IRB #: STU00204759

The research coordinator will contact the appropriate gynecologic surgeons who will introduce the study to potential participants during the pre-operative office visit. On the day of surgery, prior to the administration of anesthetics, the patient will be asked of their willingness to participate in the study, and a study member will explain the risks and benefits. A written informed consent form will be filled out. Participants will be randomized through the use of Excel to generate randomization numbers to either experimental antiseptic, chlorhexidine gluconate, or the control, povidone iodine.

STUDY TIMELINES:

Participants will be involved in the study on the day of their surgery to 24-48 hours after surgery.

The proposed timeline of the study can be seen below:

- April- June 2017: Communicate with gynecologic surgeons operating at Prentice Women’s Hospital to gain awareness for the study. Communicate with preoperative nurses and operating room circulating nurses to make them aware of the logistics of study.
- July-February 2018: Recruit and enroll patients. Administer patient surveys.
- March- September 2018: Compile and analyze data

STUDY ENDPOINTS:

List of study variables to be collected:

Outcomes	Type	Definition
Vaginal dryness	Ordinal	Any sensation of dryness in the vagina
Vaginal burning	Ordinal	Any sensation of burning in the vagina
Vaginal itchiness	Ordinal	Any sensation of itchiness in the vagina
Unusual vaginal discharge	Ordinal	Any witness of unusual discharge coming from the vagina
Pain or burning with urination	Ordinal	Any sensation of pain or burning with urination

Exposures	Type	Definition

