Pre-op chlorhexidine gluconate	Dichotomous	If women randomized to receive chlorhexidine gluconate, then yes. If woman randomized to povidone iodine, then no.

Covariates	Type	Definition
-------------------	-------------	-------------------

Woman's Age	Continuous	Female age in years at time of surgery
Surgery	Nominal	Hysteroscopy, dilation and curettage, endometrial ablation or Essure.

Other	Type	Definition	Use
Gravidity	Count	Number of prior pregnancies	Table 1 population characteristic
Parity	Count	Number of pregnancies carried to a viable gestational age	Table 1 population characteristic
Race	Categorical	Group by race: White, Black/Africa-American, Hispanic, Asian/Pacific Islander, American Indian/Alaskan Native, Middle-Eastern	Table 1 population characteristic

PROCEDURES INVOLVED:

This is a single-blinded randomized control trial. The patients will be blinded to whether they receive the control povidone iodine or the experimental chlorhexidine gluconate antiseptic. The surgeons will be aware of the treatment, but will not be administering the survey questions to minimize bias.

Given the nature of the procedures included in the inclusion criteria, participants will present to the hospital on the day of their surgery and most will be discharged two to three to hours after surgery. Participants are expected to respond to the survey pre-operatively, prior to discharge from the hospital, and 24-48 hours after surgery. This corresponds to three total surveys per participant. The first two surveys done preoperatively and prior to discharge will be done on paper. A study member via phone will administer the third survey 24-48 hours after surgery. See Appendices 1 and 2 for sample pre-operative and post-operative surveys, respectively. The survey is six questions long, and should take no longer than 3-5 minutes to administer. The survey was designed using the PRO-CTCAE (Patient- Reported Outcomes version of the Common Terminology Criteria for Adverse Events) created by the NIH/NCI. The PRO-CTCAE is a measurement system used in cancer clinical trials to detect symptomatic adverse events. The language and format of the questions have been cognitively tested.¹¹ Questions 1,4,5, and 6 are part of the PRO-CTCAE question bank. Questions 2 and 3 on the survey were investigator-developed items to capture vaginal burning and itchiness, which are not contained in the PRO-CTCAE item library.

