Appendix 1: Pre-operative survey

Date ___/___/___ Surgeon _____ Participant ID _____

Pre-operative Survey

Welcome to Northwestern Prentice Women’s Hospital. Thank you for participating in a survey being conducted by [name] on the tolerance of chlorhexidine gluconate or povidone iodine vaginal cleansing solutions. Below are questions asking about any vaginal symptoms.

Please think back over the past 7 days...

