Appendix 2: Post-operative survey

Date ___/___/___ Surgeon _____ Participant ID _____

Post-operative Survey

Thank you for participating in a survey being conducted by [name] on the tolerance of chlorhexidine gluconate or povidone iodine vaginal cleansing solutions. Below are questions asking about any vaginal symptoms.

Please think back from immediately after your surgery to now....

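### The pre-operative symptom survey has no role in the analysis, so persisting symptoms count as post-treatment symptoms in either arm; the cost is precision, not bias

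*Combined protocol and SAP*

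**What the plan says.** PROCEDURES INVOLVED schedules three surveys: "Participants are expected to respond to the survey pre-operatively, prior to discharge from the hospital, and 24-48 hours after surgery". Appendix 1 (pre-operative) and Appendix 2 (post-operative) contain the same five symptom items with the same response scales, plus an open item for other symptoms. The recall window differs: "Please think back over the past 7 days" before surgery, and "Please think back from immediately after your surgery to now" after it.

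STUDY ENDPOINTS then gives what it calls a "List of study variables to be collected":

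- Outcomes: five ordinal symptoms, defined in the style of "Any sensation of burning in the vagina". No time point is given, and nothing requires the symptom to be new or worse than before surgery.
- Covariates: two only, age ("Female age in years at time of surgery") and type of surgery.
- Other: gravidity, parity and race, each marked "Table 1 population characteristic". Pre-operative symptoms are not among them.

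STUDY ANALYSIS PLAN names one method, a two-sided test of a difference between proportions, to size the trial: irritation of 10% with povidone iodine and 31% with chlorhexidine, 80% power, 5% significance, 68 women per group after an unquantified allowance for loss to follow-up. The aims and the hypothesis, under OBJECTIVES, refer to symptoms after treatment, which fixes timing but not change from baseline.

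**The concern.** The trial asks every woman about the same symptoms before she is exposed to either antiseptic, and the plan does not use the answers. The post-operative window runs from the end of surgery, so a symptom that was there before and continues is reported again and counted, whichever antiseptic was used.

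Enrolment does not clearly keep such women out. The exclusion reads "have a history of atopic dermatitis, vaginal irritation, allergic reactions, or anaphylaxis to chlorhexidine gluconate or povidone iodine", and it can be read as covering only past reactions to the two products, which is how the Contraindications list puts it. On any reading, unusual discharge and pain on urination are not exclusions.

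At stake are the precision of the between-arm comparison and its protection against a chance difference in pre-operative symptoms. Whether planned power is also affected depends on what the 10% and 31% stand for, which the protocol does not say.

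**Working it through.** **Inputs.** From STUDY ANALYSIS PLAN: 10% and 31%, two-sided 5%, 80% power, 68 per group. Assumed, because the documents give no figure: pre-operative prevalence *b* of 10%, 20% or 30%; persistence *s* (the chance that a pre-operative symptom is still present after surgery) of 25%, 50% or 80%.

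**1. The plan's own figure.** With the pooled formula, n = [1.960·√(2·0.205·0.795) + 0.842·√(0.10·0.90 + 0.31·0.69)]² / 0.21² = (1.119 + 0.464)² / 0.0441 = 56.8, so 57 per arm. 57/0.85 = 67.1, so 68. The stated 68 is reproduced with about 15% to 16% loss. Power is 80.1% at 57 per arm and 86.7% at 68. The rest uses 57 evaluable per arm.

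**2. Chance imbalance.** With X₁ and X₂ independent Binomial(57, *b*), the probability that |X₁ − X₂|/57 is at least 0.10 is 8.5%, 19.7% and 26.1% for *b* = 10%, 20% and 30%.

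**3. Model for persistence.** Let *k* = *b*·*s*, the share of women with a persisting symptom, equal in expectation in both arms. A woman has a post-operative symptom if one persists or one is induced, so total = *k* + (1 − *k*)·induced.

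*Reading 1: 10% and 31% are totals, background included.* The totals do not move, so unadjusted power does not move (simulated 81% to 82%). This is possible only if *k* is at most 10%. The induced rate is (total − *k*)/(1 − *k*).

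*Reading 2: 10% and 31% are antiseptic-induced rates.* The difference shrinks to 21·(1 − *k*) points. For *b* = 20% and *s* = 80%, *k* = 0.16, the totals are 24.4% and 42.0%, and the gap is 17.6 points.

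**4. Unadjusted test against a Mantel-Haenszel test stratified by pre-operative symptom.** Simulation, 57 per arm; results are good to about a point.

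| Reading | Persistence | *b* | Unadjusted power | With stratification |
|---|---|---|---|---|
| 1 | 25% | 10/20/30% | 81–82% | gain of about 0–2 points |
| 1 | 50% | 10/20% | 82% | gain of about 4–9 points |
| 1 | 80% | 10% | 82% | 94%, gain of about 12 points |
| 2 | 25% | 10/20/30% | 76/71/66% | gain of about 1 point or less |
| 2 | 80% | 10/20/30% | 65/54/42% | 75/69/60% |

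The largest gains under Reading 1 come from settings where almost all povidone iodine symptoms are background. At *b* = 10%, *s* = 80% the induced povidone iodine rate is (0.10 − 0.08)/0.92 = 2.2%; at *b* = 20%, *s* = 50% it is (0.10 − 0.10)/0.90 = 0%.

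**5. Size of the tests.** With no true difference, the unadjusted test stays near 5%. The stratified Mantel-Haenszel test stays at about 4% to 5.5%. A logistic likelihood-ratio test with the pre-operative symptom as covariate runs from 5% to 8%, the highest value at *b* = 10%, *s* = 80% under Reading 1. Part of any power gain from that test is therefore inflated size.

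**The case against.** The strongest reply is that randomisation already deals with background symptoms. It does, as far as bias and type I error go. A reader might infer from the unused baseline that the comparison is biased, or that false positives rise; neither follows. What remains is precision and chance imbalance.

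A second reply is that the damaging power figures rest on the less natural reading and on assumed inputs. This largely stands. The protocol speaks of the prevalence of irritation in each group, which most naturally includes background symptoms, and then planned power is intact. A reader might also infer that dilution pushes the trial towards its hypothesis of no significant difference. That requires the planning figures to be induced rates, and the loss is severe only if pre-operative symptoms are common and mostly persist. The documents show none of this.

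A third reply is that the variable list is not a full analysis specification: surgeon, cystoscopy and catheter use are also collected without a stated use, and the outcome rows, having no time point, could be said to cover the pre-operative answers too. That is fair, but listing an item as an outcome does not say how its pre-operative value enters the comparison.

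Finally, the version date (5/09/18) falls in the period that STUDY TIMELINES sets aside for analysis, so a reader might infer that outcomes had already been seen. The documents do not establish this: the two-weekly data review appears under safety monitoring, and the paper-storage sentence can be read as data collection running to September 2018.

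**Conclusion.** The omission is certain: no section gives the pre-operative answers a use, and the outcome definitions do not separate persisting from new symptoms. The size of its effect is not known. Under the more natural reading of the planning figures the consequence is forgone precision, from next to nothing at low persistence to about 12 points of power in an extreme setting. Under the other reading it is a loss of planned power that stratifying recovers in part at high persistence and hardly at all at low. Every such figure depends on assumed prevalence and persistence and on 57 evaluable women per arm. High confidence attaches to the omission only. It should be corrected because the remedy is cheap and the data are collected anyway, not because the trial is shown to be invalid or underpowered.

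**What to change.** 1. Keep the planned difference in proportions, and stratify each between-arm comparison by the matching pre-operative symptom (present or absent), with a Mantel-Haenszel test and risk difference. Do not rely on a logistic likelihood-ratio test at a nominal 5%. For the five-level severity items, use a proportional-odds model with the pre-operative score, and check its small-sample size. Models that add the listed covariates, age and type of surgery, can be reported alongside.
2. Name which of the two post-operative surveys is the main time point.
3. Report pre-operative symptoms by arm in Table 1. Report new or worsened symptoms as a named secondary outcome, noting that recall covers 7 days before surgery but only hours to 2 days after it.
4. State whether the 10% and 31% include background symptoms.
5. If outcome data were examined before this change, label the adjusted analysis as added later.

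The cost is a few sentences in the plan and a little more analysis work. No new data are needed.

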The data to be collected will include: age, gender, race, gravidity, parity, surgeon, type of surgery, concomitant cystoscopy, use of Foley catheter, name of antiseptic solution, and presence and severity of vaginal and urinary symptoms based off survey responses. The patients will receive preoperative vaginal preparation either with povidone iodine or

chlorhexidine gluconate. Both antiseptic solutions are approved for surgical preparation of the vagina at Northwestern's Prentice Women's Hospital.

DATA & SPECIMEN MANAGEMENT:

Paper data will be stored in a locked cabinet at the nursing desk of the preoperative holding area and periodically transferred to a password protected Excel file on a password-protected laptop. Paper surveys will be stored for 1 years after the end date of the data collection (September 2019) and will be discarded through the hospital's confidential document shredding service. Electronic data will be de-identified and stored indefinitely on a password-protected computer.

The data will be transitioned to Excel and analyzed with a statistical software like SPSS. The participant's MRN will be collected in order to link survey data with patient demographics and the corresponding surgery/vaginal cleansing intervention. This MRN will be matched to a participant ID, and the survey will only have the patient's ID on it. The document linking MRN with participant ID will be kept separate from the surveys. The data collection spreadsheet will not contain patient MRNs.

PROVISIONS TO MONITOR DATA TO ENSURE THE SAFETY OF PARTICIPANTS:

The PI, [name], and researchers, [name], [name], [name], and one other research coordinator will have access to the data. The study team will evaluate the data collected every 2 weeks, and look at any adverse events to ensure patient safety. Safety information will be collected with case report forms. The Principal Investigator will be notified within 24 hours of learning of any serious adverse events, regardless of attribution, occurring during the study. The office of Risk Management and the IRB will be notified as soon as possible of "any unanticipated problems involving risk to subjects or others" (UPR/UPIRSO).

Contraindications:

Contraindications include patient with a history of the following after use of chlorhexidine gluconate or povidone iodine in any application:

- Atopic dermatitis
- Vaginal irritation
- Allergic reactions
- Anaphylaxis

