The incidence of these events has not been studied specific to vaginal application.

Special Warnings and Precautions for Use:

There is a FDA warning of severe allergic reactions with chlorhexidine gluconate. Chlorhexidine gluconate continues to be used preoperatively as antiseptic agent at Northwestern operating rooms.

Chlorhexidine Gluconate and Povidone Iodine

- Do not use in contact with meninges, or over skin of head or face.
- Stop use if irritation, sensitization, or allergic reaction occurs.
- Keep out of eyes, ears, and mouth. May cause serious and permanent eye injury if placed or kept in the eye during surgical procedures or may cause deafness when instilled in the middle ear through perforated eardrums.
- If solution should contact these areas, rinse out promptly and thoroughly with water

IRB #: STU00204759

- Wounds which involve more than the superficial layers of the skin should not be routinely treated
- Repeated general skin cleansing of large body areas should not be done except when the underlying condition makes it necessary to reduce the bacterial population of the skin.

Interaction with other medications:

No studies of interactions between chlorhexidine gluconate and povidone iodine and other drugs have been conducted.

Adverse Reactions:

The FDA reports the following possible side effects with the active medications

Chlorhexidine Gluconate:

- Severe allergic reactions (rash; hives; itching; difficulty breathing; tightness in the chest; swelling of the mouth, face, lips, or tongue). It is possible that some side effects of chlorhexidine gluconate have not been reported.

Povidone Iodine:

- Severe allergic reactions (rash; hives; itching; difficulty breathing; tightness in the chest; swelling of the mouth, face, lips, or tongue). It is possible that some side effects of povidone iodine topical may not have been reported.

Adverse Event Monitoring:

Adverse event data collection and reporting, which are required as part of every clinical trial, are done to ensure the safety of Subjects enrolled in the studies as well as those who will enroll in future studies using similar agents. Adverse events are reported in a routine manner at scheduled times during a trial. Additionally, certain adverse events must be reported in an expedited manner to allow for optimal monitoring of patient safety and care. The following events meet the definition of adverse event:

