1. Any serious event (injuries, side effects, deaths or other problems), which in the opinion of the Principal Investigator was unanticipated, involved risk to subjects or others, and was possibly related to the research procedures.
2. Any serious accidental or unintentional change to the IRB-approved protocol that alters the level of risk.
3. Any deviation from the protocol taken without prior IRB review to eliminate apparent immediate hazard to a research subject.
4. Any new information (e.g., publication, safety monitoring report, updated sponsor safety report), interim result or other finding that indicates an unexpected change to the risk/benefit ratio for the research.
5. Any breach in confidentiality that may involve risk to the subject or others.
6. Any complaint of a subject that indicates an unanticipated risk or that cannot be resolved by the Principal Investigator.

All other adverse events- such as those that are expected, or are unlikely or definitely not related to the study participation- are to be reported annually as part of regular data submission.

WITHDRAWAL OF PARTICIPANTS:

Participants will be withdrawn from the study without their consent if the patient experience anaphylaxis from either of the antiseptics, if the patient becomes pregnant, if

the physician decides participation in the study is not in the patient's best interest, and if the planned procedure is unable to be completed. These events will be recorded and stated when presenting data from the study.

RISKS TO PARTICIPANTS:

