There are possible side effects to both chlorhexidine and povidone iodine. These include atopic dermatitis, vaginal irritation, allergic reactions, and anaphylaxis. There is a FDA warning of severe allergic reactions with chlorhexidine gluconate. Chlorhexidine gluconate routinely to be used preoperatively as antiseptic agent at Northwestern operating rooms. A review of anesthesia drug safety literature showed in patients who had allergic reactions after general anesthesia, chlorhexidine accounted for 5% of the allergies. Additionally, patch testing for chlorhexidine revealed a positive test in 2% of the participants suspected of contact allergic dermatitis exposed to chlorhexidine after topical application. It is estimated that this percent increases to greater than 5% in patients with atopic dermatitis, and thus patients with atopic dermatitis will be excluded in this study.¹² In another study looking at 50 cases of allergic reactions to chlorhexidine, 9 were found to have anaphylaxis.¹³ In regards to povidone iodine, one study looked patients who had a rash after exposure to povidone iodine and found 10% to have a positive patch test.¹⁴ There have been multiple case reports of anaphylaxis to povidone iodine, but no particular statistic has been reported.¹⁵ The exact incidence of the adverse events of either antiseptic in the general population still remains unknown, as well the incidence of these events with vaginal application.

POTENTIAL BENEFITS TO PARTICIPANTS:

There is no direct benefit to participants.

SHARING OF RESULTS WITH PARTICIPANTS:

The results of the study are patient-reported outcomes. Patients will not be informed on the overall study results.

SETTING:

The research study will take place at Northwestern's Prentice Women's Hospital. Antiseptic procedures will occur at Prentice operating rooms prior to surgery.

RESOURCES AVAILABLE:

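### A list of expedited-report problems is labelled as the adverse event definition; it conflicts with the rest of the protocol, and expected or non-serious reactions seen by staff may go unrecorded by arm

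*Combined protocol and SAP*

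**What the plan says.** All references are to the combined protocol and SAP.

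- **Adverse Event Monitoring, opening paragraph.** It first announces a subset: "Additionally, certain adverse events must be reported in an expedited manner to allow for optimal monitoring of patient safety and care". It then introduces six items with "The following events meet the definition of adverse event".
- **Item 1** covers a serious event "which in the opinion of the Principal Investigator was unanticipated, involved risk to subjects or others, and was possibly related to the research procedures".
- **Items 2 to 6** cover other matters. Item 3 is "Any deviation from the protocol taken without prior IRB review to eliminate apparent immediate hazard to a research subject" and item 5 is "Any breach in confidentiality that may involve risk to the subject or others".
- **The closing sentence after the list** deals with all remaining adverse events, giving expected and unrelated ones as examples. These "are to be reported annually as part of regular data submission".
- **Risks to Participants** describes the possible side effects of both antiseptics: "These include atopic dermatitis, vaginal irritation, allergic reactions, and anaphylaxis".
- **Provisions to Monitor Data to Ensure the Safety of Participants** has the study team evaluate the collected data every 2 weeks and "look at any adverse events to ensure patient safety". Safety information goes on case report forms. The principal investigator is told of every serious adverse event within 24 hours, whatever its cause. The IRB and Risk Management are told promptly of unanticipated problems.
- **Withdrawal of Participants** lists anaphylaxis and an uncompleted procedure among the reasons for withdrawal, and says these events will be recorded and reported with the results.

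**The concern.** A definition of adverse event tells staff what to write down. The one given here is a list of problems for expedited reporting, and the sentence that closes the section assumes a wider class that the definition does not contain. Staff cannot follow both.

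Tolerance is the trial's question, and the reactions of most interest are the ones the protocol already expects. If staff apply the list literally, a rash or visible mucosal change noticed in the operating room has no category on the case report form. The two arms could not then be compared on it. Separately, a serious reaction judged expected has no stated prompt route outside the study team.

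**Working it through.** The check is mainly textual, with one calendar count at the end.

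**1. What each item requires.**

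| Item | Subject | Must be serious? | Must be unanticipated? | Route for a clinical reaction? |
|---|---|---|---|---|
| 1 | An event in the study | Yes | Yes, in the principal investigator's opinion | Yes, if also risk-involving and possibly related |
| 2 | Unintended change to the approved protocol | Yes (the change) | Accidental or unintentional | No |
| 3 | Deviation made to avert a hazard | No | No | Indirect only |
| 4 | New information on risk and benefit | No | The change must be unexpected | Indirect, for a pattern of reactions |
| 5 | Confidentiality breach | No | No | No |
| 6 | Participant complaint | No | One limb only; the other is that it cannot be resolved | Only if the participant complains |

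Item 1 is the only direct route.

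**2. Applying item 1 to the reactions under Risks to Participants.**

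- Non-serious reaction: fails item 1, expected or not.
- Serious reaction judged expected: fails item 1.
- Serious reaction judged unanticipated and possibly related: meets item 1.

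The choice between the last two is left to the principal investigator. The protocol says the incidence of these events with vaginal application has not been studied, so exclusion is likely for a named reaction but not automatic.

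**3. The conflict.** If the list is the definition, there are no other adverse events for the closing sentence to route. If the closing sentence is right, the list is only the expedited subset that the preceding sentence announced, and the label is wrong. The safety monitoring section, which speaks of any adverse event and of serious ones without restriction, fits the second reading. Under either reading, nothing states what an adverse event is in general.

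**4. What the surveys cover.**

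- Appendix 1 (before surgery) looks back 7 days, so it precedes the antiseptic.
- Under Setting, the antiseptic is applied in the operating room before surgery.
- Appendix 2 (before discharge and at 24-48 hours) asks about the time from just after surgery onward.

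The interval from application to the end of surgery is in neither recall period. A symptom that persists can still be reported afterwards. A sign that only staff see, or that resolves, depends on the case report form and so on the definition. The Background cites a case of desquamated vaginal epithelium that led to cancelled surgery. Here an uncompleted procedure would count as a withdrawal and be recorded; a milder reaction that did not stop surgery would not be caught that way. The protocol plans no adverse event table by arm.

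**5. Who hears of what, and when.**

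| Event | Principal investigator | Study team | IRB and Risk Management |
|---|---|---|---|
| Serious, unanticipated | 24 hours | 2 weeks | Promptly |
| Serious, judged expected | 24 hours | 2 weeks | No prompt route stated |
| Non-serious, reported in survey | Not stated separately | 2 weeks, as collected data | No prompt route stated |
| Non-serious, seen only by staff | Not stated separately | 2 weeks, if recorded | No prompt route stated |

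**6. Timing of an annual report.** Study Timelines plans enrolment from July (read as 2017) to February 2018: 6 + 2 = 8 months, the upper end of the 6 to 8 months in the Study Analysis Plan. The start of the annual clock is not given. Assuming 1 April 2017, the first report falls on 1 April 2018, 32 days after 28 February 2018. Assuming 1 July 2017, it falls on 1 July 2018, 123 days after. An anniversary between July and February would fall inside the enrolment window.

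**The case against.** The best defence is that this is one mislabelled sentence. The sentence before it announces a subset for expedited reporting, the list reads like that subset, and the closing sentence plainly treats expected reactions as adverse events. On that reading the two-weekly review covers them as well. One cannot argue both that expected reactions are outside the term, and so escape the review, and that they are inside it, and so go to the annual report. Moreover, the review covers the collected data as a whole, including graded symptoms and the antiseptic used. Survey question 6 invites other symptoms. Case report forms are planned. Item 4 could catch an unexpected excess of known reactions.

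Most of this stands. It shows that patient-reported irritation is monitored whatever the definition says, and that the probable intention is sound. It does not supply a definition for the case report form, cover signs that only staff see before surgery ends, or give a prompt external route for an isolated serious reaction judged expected.

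**Conclusion.** The point holds as a defect of definition with two limited consequences. First, expected or non-serious reactions seen by staff between antiseptic application and the end of surgery may go unrecorded by arm, apart from those that lead to withdrawal. This assumes that staff follow the definition literally. Second, no section gives a prompt report to the IRB or Risk Management for a serious reaction judged expected. No endpoint, sample size or planned comparison changes. The text should be corrected, but the trial's main question does not depend on it.

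A reader might infer three stronger things, none of which the documents support:

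- **That the list admits only serious, unanticipated problems.** Items 3 and 5 and one limb of item 6 require neither.
- **That anaphylaxis is left to an annual report.** As a serious event it reaches the principal investigator within 24 hours, and it is a withdrawal that is recorded and reported. Whether it counts as unanticipated is a matter of judgement.
- **That the annual report necessarily comes after enrolment.** This depends on a start date that is not given. The protocol version is also dated 5/09/18, later than the planned close in February 2018, so the actual enrolment dates are uncertain.

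**What to change.** 1. Define an adverse event as any untoward medical occurrence from antiseptic application to the 24-48 hour survey, whether or not serious, expected or related.
2. Relabel the six items as problems requiring expedited reporting.
3. Record all adverse events on the planned case report forms, including those seen by staff before surgery ends, and tabulate them by arm.
4. Reconcile the opening of Adverse Event Monitoring, its closing sentence on annual reporting, and the safety monitoring section, so that the route for a serious but expected reaction is stated once and consistently.

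The cost is protocol wording, slightly more recording on forms already planned, and one table.
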